#### 9.2.1 Treatment Assignment Procedures

The unit of randomization will be the primary care practice or team. We anticipate 32 out of 39 teams from USMM to meet eligibility and 26 out of 28 practices for Ochsner. Within each ACO, we will randomly select half of the practices for participation in the value champion training and the remaining practices will continue with care as usual. Prior to random assignment, we will stratify practices based on high versus low historic prescribing rates. We will select practices for randomization and inclusion using a cut-point based on the distribution of overall rates for all 3 therapeutic classes using data for 2019-2020. Once randomized, a clinician value champion will be recruited from each of the clinics randomized to the intervention arm of the study in partnership with the ACO leadership.

### 9.3 Interim analyses and Stopping Rules

N/A – No interim analyses are planned. The proposed activities involve the collection and analysis of secondary automated system patient data for Specific Aims 1 & 2, and interviews with clinician value champions for Specific Aim #3.

### 9.4 Outcomes

#### 9.4.1 Primary outcome

The primary outcome for this study (Specific Aim #1) will be medication possession rates (MPR) per quarter, for the 3 therapeutic classes of medications - antipsychotics, benzodiazepines, and hypoglycemics - that are considered low-value for beneficiaries with dementia. These beneficiary-level measures are calculated as quotients with denominator equal to the length of the quarter and the numerators equal to the days supply for prescriptions within the class filled during the quarter, plus excess days-supply from the previous period minus excess days-supply remaining at the end. Unlike many studies using medication possession rates to exam adherence, we are interested in reducing, not increasing, the percent of days covered. As a first choice, we will try to use originally-valued MPR variables in regression modeling, but if they don't reflect adequate

fit, we will transform them or possibly convert them to ordinal variables instead. For example, Benner and colleagues in their study of statin adherence defined non-adherence as MPRs within 0-20 percent, low-adherent as between 21-79 percent and high adherence as 80 percent or higher. In addition to MPRs, we will also calculate and analyze the number of 30-day prescriptions per time-period for each beneficiary in the study.

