### Sample Size and Population

Medicare beneficiaries from claims data provided by each ACO will be included in the final outcome analysis if they meet all of the following criteria prior to the start of the intervention: a) they are seen by a clinician at a participating clinic as evidenced by one or more evaluation and management claims, b) they have continuous coverage in Medicare Parts A, B and D and no months of Part C (Medicare Advantage), and c) they have two or more claims with an ICD-10 diagnosis for Alzheimer's or Alzheimer's related dementia 30 days apart or 1 inpatient stay with a principal diagnosis of Alzheimer's. We anticipate a total of approximately 5,000 patients will be included in this final analysis across both ACOs.

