## **4 SELECTION AND ENROLLMENT OF PARTICIPANTS**

### **4.1 Inclusion Criteria**

Clinician practices within two ACOs will be eligible for participation in the study if they meet the following criteria:

- a. They include 3 or more primary care providers (defined as a primary care physician (specialty code of 08 or 11), nurse practitioner (specialty code = 50) or physician's assistant (specialty code = 97)) and
- b. They have clinical encounters with 10 or more Medicare beneficiaries with Alzheimer's or Alzheimer's related dementia in the base years (2019-2020).

Medicare beneficiaries will be included in the study if they meet all of the following criteria during the intervention year:

- a. They are seen by a clinician at a participating practice as evidenced by one or more evaluation and management claim,
- b. They have continuous coverage in Medicare Parts A, B and D and no months of Part C (Medicare Advantage),
- c. They have two or more claims with an ICD-10 diagnosis for Alzheimer's or Alzheimer's related dementia 30 days apart or 1 inpatient stay with a principal diagnosis of Alzheimer's.

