### **7.2 Methods and Timing for Assessing, Recording, and Analyzing Safety Parameters**

As data used to measure the primary outcome is de-identified, contains no PHI, and is collected after the intervention is completed. However, to ensure that we capture any unexpected AEs, we will ask each clinician champion to monitor for any unexpected adverse events and complete an adverse event form if they see one. Once each month, clinician value champions will be asked to send all adverse event forms to the study coordinator. No SAEs are expected as described above. All deaths within the study cohort will also be reported along with a cause of death

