## **9 STATISTICAL CONSIDERATIONS**

### **9.1 General Design Issues**

Our hypothesis is that for each medication class, the intervention will produce clinically relevant decreases in mean possession rates of 10% of a standard deviation in patients seen in intervention clinics compared to those who are seen in control group clinics.

The study design was chosen to meet the requirements of the funder for a non-pharmacologic/non-device intervention for people living with dementia, conducted in a health system setting. The 24-months of funding is for a demonstration project, intended to demonstrate the feasibility and acceptability of the intervention, but with the stipulation by the funder that the trial must be a randomized controlled trial, one with a control group. In response, we proposed a cluster-randomized trial where the intervention will be randomized at the primary care clinic level, not the patient level, and existing health systems claims data will be used to address our primary outcome (Specific Aim #1) and one of our secondary outcomes: Specific Aim #2: emergency department visits and hospitalizations for a fall.

The primary outcome measure for this study will be medication possession rates (MPR) per quarter, for the 3 therapeutic classes of medications - antipsychotics, benzodiazepines, and hypoglycemics - that are considered low-value for beneficiaries with dementia. Unlike many studies using medication possession rates to exam adherence, we are interested in reducing, not increasing, the percent of days covered. Following an intent-to-treat design, claims data from all Medicare beneficiaries meeting our dementia eligibility criteria prior to the start of the value champion intervention will be included in the analysis. To determine the impact of the intervention, we will construct hierarchical models with time period observations nested within patient. These models will be random effects or generalized estimating equations (GEE) with robust standard errors, and will be either linear, if original MPRs are used as outcome, or generalized linear, if transformation necessary. The key variable of interest in these models will be the treatment indicator (assigned based on practice randomization to intervention or control group).

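### The primary MPR divides by the full quarter with no rule for quarters cut short by death, and two conflicting eligibility windows leave loss of coverage unsettled

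*Combined protocol and SAP*

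**What the plan says.** **Outcome.** Section 9.4.1, and section 3 under Specific Aim #1, define the MPR for each patient, drug class and quarter as a quotient with "denominator equal to the length of the quarter". The numerator is the days' supply filled in the quarter, "plus excess days-supply from the previous period minus excess days-supply remaining at the end". Section 9.4.1 adds that a lower value is the aim.

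**Who is analysed.** The plan gives two windows.
- The précis (Sample Size and Population) includes beneficiaries "if they meet all of the following criteria prior to the start of the intervention", and continuous Parts A, B and D coverage is one of those criteria. Section 9.1 says that all beneficiaries "meeting our dementia eligibility criteria prior to the start of the value champion intervention will be included in the analysis"; it does not repeat the coverage criterion.
- Section 4.1, like Study Population in section 3, includes them "if they meet all of the following criteria during the intervention year", again with continuous coverage and no Part C. Section 6.2.1 (Screening) places screening in months 1 to 3, before the intervention, yet applies eligibility during the intervention year.

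**Deaths.** Section 7.2 states: "All deaths within the study cohort will also be reported along with a cause of death". This is safety reporting. The hospice exclusion in 4.2 looks back six months from the start and does not remove later deaths. Section 9.2 counts about four quarterly observations per patient with no allowance for death or loss of coverage.

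No section says how to score the quarter of death, the quarters after it, or a quarter with partial coverage.

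**The concern.** In a dementia cohort followed for a year, some quarters will be cut short by death. With a fixed full-quarter denominator, a patient who used the drug until death can score below a patient who used it for the whole quarter, although prescribing did not change. Because lower MPR is favourable, the error runs in the direction the trial hopes to see.

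Three features of the plan make this more than a definitional nicety.
- The Study Rationale lists death and hospital admission among the harms of these drugs, so a mortality difference between arms is possible on the protocol's own reasoning. Fewer deaths in the intervention arm would mask a true reduction in prescribing; more would imitate one.
- Section 9.5 will use time terms and treatment-by-time interactions to look for gradual trends. If quarters after death are scored zero, deaths accumulate and produce a downward trend by themselves.
- Section 9.4.1 allows an ordinal fallback and gives cut-points of 20% and 80% as an example. A score of 0.67 would move a continuous user from the top category to the middle one.

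For loss of coverage, what happens depends on which eligibility window the analyst applies, and that choice could be made after the data are seen.

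**Working it through.** **1. The plan's own power figures.** From section 9.2: 2,000 × 0.8 = 1,600 effective observations per group (Ochsner), 8,000 × 0.8 = 6,400 (USMM), effect 0.10 SD, 5% level (two-sided assumed; the plan does not say). Power = Φ(δ√(n/2) − 1.96).
- Ochsner: 0.10 × √800 = 2.828; Φ(0.868) = 0.807. Stated: 80%.
- USMM at 0.10 SD: 0.9999. At 0.05 SD: 0.807. Stated: almost 100% and 80%.

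The stated figures reproduce, taking the 20% reduction as given.

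**2. One patient.** A continuous user in a 90-day quarter, fills starting on day 1, no carry-in. With L-day fills and death on day x, literal MPR = min(L × ⌈x/L⌉, 90)/90. The numerator subtracts only supply left at the end of the quarter, so supply in hand at death still counts.

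| Death on day | 30-day fills | One 90-day fill | Days-alive denominator, supply capped at death |
|---|---|---|---|
| 15 or 30 | 0.33 | 1.00 | 1.00 |
| 45 or 60 | 0.67 | 1.00 | 1.00 |
| 75 | 1.00 | 1.00 | 1.00 |

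**3. Cohort mean.** The documents give no mortality rate, fill length or adherence among users. Assumptions: annual mortality m of 10 to 20%, deaths spread evenly over four quarters, users fully supplied while alive, fills aligned to quarters. A patient who dies then has on average (0+1+2+3)/4 = 1.5 complete quarters, one part quarter and 1.5 later quarters. Let f be the mean score in the part quarter: 1/2 if no supply counts beyond death, (1/3+2/3+1)/3 = 2/3 with 30-day fills, 1 with a 90-day fill.
- Later quarters dropped: understatement U = m(1 − f)/(4 − 1.5m).
- Later quarters zero: U = m(2.5 − f)/4.

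| Supply pattern | Later quarters dropped, m = 10% / 20% | Later quarters zero, m = 10% / 20% |
|---|---|---|
| None beyond death | 1.3% / 2.7% | 5.0% / 10.0% |
| 30-day fills | 0.9% / 1.8% | 4.6% / 9.2% |
| 90-day fill | 0% / 0% | 3.75% / 7.5% |

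**4. Difference between arms.** Treat MPR as user/non-user with prevalence p, so the SD is √(p(1 − p)). The spurious difference in SD units is (U₁ − U₀) × √(p/(1 − p)), where U₁ belongs to the arm with higher mortality. With equal mortality it is zero. At p = 14.3% (the antipsychotic figure in section 2.1) the multiplier is 0.4085. For an assumed 15% versus 20% mortality:
- Later quarters dropped, 30-day fills: (0.01802 − 0.01325) × 0.4085 = 0.002 SD. With 90-day fills it is zero.
- Later quarters zero, no supply beyond death: (0.100 − 0.075) × 0.4085 = 0.010 SD.
- Extreme case, 10% versus 20%, later quarters zero, p = 35.2% (a sulfonylurea figure in section 2.1 from patients with A1c below 7%, borrowed only as a high value): (0.10 − 0.05) × 0.737 = 0.037 SD.

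**5. Trend over time.** If later quarters are zero and no supply counts beyond death, the share of time lost is m/8 in quarter 1 (1.3 to 2.5%) and 7m/8 in quarter 4 (8.8 to 17.5%).

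**6. Power.** In that same worst case, 0.10 SD becomes 0.095 to 0.090 SD with the SD held fixed, and Ochsner power is 0.766 to 0.721. The added zeros also shrink the SD. At p = 14.3% and 10% loss it is √(0.1287 × 0.8713) = 0.335 against 0.350, so the effect is 0.10 × 0.350 × 0.90/0.335 = 0.094 SD. For 5% loss it is 0.097 SD. Power is then about 76 to 78%. Leaving the dead time out instead cuts 1,600 to 1,520 or 1,440 and gives 0.787 or 0.765. Power therefore does not distinguish the two treatments of death.

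**The case against.** The strongest reply is that the plan is silent on incomplete quarters, and silence is not a rule. The formula describes an ordinary quarter. Random-effects and GEE models do not need four quarters per patient, so an analyst could reasonably stop at death, and the understatement is then at most 2.7%. Section 4.1 removes patients who lose Part D or join Part C during the intervention year. Deaths occur in both arms, so with equal mortality the result is mild dilution. The proposed remedy also has a price: restricting to time alive and covered conditions on events after randomisation.

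Much of this stands, and it rules out several stronger readings that a reader might infer.
- That the plan scores every death as zero use: no section says that quarters after death are kept.
- That a patient dying on day 45 scores 0.50: this needs supply to run out on the day of death, whereas the stated numerator counts supply past it.
- That disenrolment is scored as reduced prescribing: this follows only under the pre-intervention window.
- That Ochsner power falls to 77 to 72%: this needs later quarters scored zero, no supply beyond death, a fixed SD and assumed mortality.

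The reply does not remove the point. The denominator is stated twice without qualification for the primary outcome, and the literal calculation can misstate use in the quarter of death. Section 4.1 does not settle coverage either. It conflicts with the précis, and it excludes patients for something that happens after randomisation. It also leaves open whether death itself breaks continuous coverage: if so, patients who die are removed; if not, the part quarter remains.

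**Conclusion.** The point holds as a defect in the definition and pre-specification of the primary outcome, of modest size. The full-quarter denominator can understate use in the favourable direction in a quarter cut short by death, and the handling of later quarters is undefined. Loss of coverage cannot be resolved until the two eligibility windows are reconciled.

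Under the assumptions in the working, the choice about later quarters matters most: mean MPR is understated by 0 to 2.7% if they are dropped and by 3.75 to 10% if they are zero. A false difference between arms requires unequal mortality or disenrolment. At 15% versus 20% mortality it is about 0.002 to 0.010 SD, or a tenth of the 0.10 SD target at most; the extreme case reaches 0.037 SD.

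A reader might infer that deaths could by themselves produce a positive trial. The documents give no mortality data to support that, and none of the scenarios examined approaches 0.10 SD. The reason to act is a valid, pre-specified measure, not recovered power. The change should be made, but the design does not fail without it.

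**What to change.** - Define the denominator as days in the quarter on which the patient was alive and covered by Parts A, B and D, with no Part C. Cap the numerator to supply for those same days.
- Treat quarters with no eligible days as not observed, and weight the remaining quarters by eligible days.
- State one eligibility window, fixed before the intervention, in the précis and sections 3, 4.1, 6.2.1, 9.1 and 9.5. Later loss of coverage then ends follow-up and no longer removes the patient.
- Carry death and coverage dates, or eligible-day counts per quarter, into the analytic file. Section 9.4.2 mentions only age and sex from the beneficiary summary files, and section 10.1 describes a de-identified file, so this must be settled before that file is built.
- Report deaths and coverage loss by arm beside the MPR result, with a sensitivity analysis that scores quarters after death as zero.

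The cost is SAP wording and a few derived variables. The downsides are that quarters of unequal length need weights, and that the estimate becomes MPR while alive and covered. That is an estimand choice conditional on events after randomisation, and the SAP should say so.

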#### 9.4.2 Secondary outcomes

As a secondary outcome, for Specific Aim #2, we will also assess the incidence of falls during the study window. Falls are difficult to monitor using claims data, but Min and colleagues have developed a method that IAC and Brandeis staff (Co-Investigator [name]) have helped test for ICD-10. We will use the most conservative definition that looks for the presence of fall ‘reason for visit’ code on ED, ambulatory, or inpatient visit as indicated by a clinician bill (Part B). Key covariates in all of our regression models will include age and sex, both derived from the Medicare beneficiary summary files, house at IAC.

For Specific Aim #3, the five important implementation outcomes: appropriateness, fidelity, feasibility, and penetration will be assessed by analyzing interviews with clinician value champions. The Clinician interviews will provide us with data we need to assess the implementation outcomes.

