### Design and Outcomes

This study is a pragmatic cluster-randomized trial to test the effectiveness of a primary care clinician value champion for de-implementing potentially inappropriate medications among patients 65 years of age and older with a diagnosis of dementia. Medicare Part D pharmacy claims data will be analyzed at the end of the 12-month intervention for the primary outcome, the medication possession rates (MPR) for three groups of potentially inappropriate medications: antipsychotic medications, benzodiazepines, and hypoglycemic medications (sulfonylureas and insulin). In a similar fashion, a hospital admission, or an emergency department visit for a fall will be assessed at the end of the intervention using Medicare claims data. Finally, the five implementation outcomes – Appropriateness, Fidelity, Feasibility, Penetration and Equity - will be evaluated through analysis of interviews conducted with participating clinician value champions.

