### **1.2 Secondary Objectives**

As a secondary outcome, we will also assess the incidence of emergency department visits or hospitalizations due to a fall during the study window.

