## **5 STUDY INTERVENTIONS**

### **5.1 Interventions, Administration, and Duration**

No drugs or devices will be studied. The intervention is a quality improvement strategy consisting of a clinician value champion who will engage other clinicians within their clinic in an effort to decrease the use of PIMs in PLWD. Typical methods of engagement include educational meetings, facilitating conversations about evidence of harm, providing current provider-specific data on rates of prescribing, etc.

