## **7 SAFETY ASSESSMENTS**

### **7.1 Specification of Safety Parameters**

There are no known risks to discontinuing these potentially inappropriate medications. Instead, the purpose of discontinuing these medications is to lower the risk of an adverse event due to the medication such as a fall, changes in cognitive status, or acceleration of the course of dementia. In addition, the data used to measure the primary outcome, pharmacy claims data, is de-identified and contains no PHI, lowering the risk due to loss of confidentiality.

These three classes of medication pose significant risks to older patients with dementia including falls, changes in cognitive status, and potentially accelerating the course of their dementia. The risk of these adverse events is significantly lowered by discontinuing these medications. Each of the risks described above also has the potential to create a cascade of adverse experiences such as fractures or head trauma from falls, resulting in hospitalization and the need for skilled nursing care instead of returning home.

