## **10 DATA COLLECTION AND QUALITY ASSURANCE**

### **10.1 Data Collection Forms**

We have two primary data sources: the 100% Medicare claims files from each ACO, and interviews with clinicians conducted by staff at KPHRI and Brandeis. . Secondary data from Medicare Part D pharmacy claims data will provide us with our primary outcome data: cumulative exposure to any of the PIMs among an inception cohort of PLWD. In addition, Medicare claims data will be used for the third exploratory aim: rates of ED visits or admissions for a fall. This data will be identified and collected by the study programmer / analyst at AIC.

The Clinician interviews will provide us with the data we need for our implementation outcomes. A interview protocol is submitted for review. Data Management

Clinical Site Responsibilities: The two participating ACO organizations have Data Use Agreements with the Institute for Accountable Care, to access their 100% Medicare Claims data for purposes of the secondary data analyses for Specific Aims #1 & 2.

The Institute for Accountable Care will be responsible for data management of the secondary Medicare claims data. Their programmers will create a de-identified analytic file for Drs. [name] and [name] to use to test hypotheses for Aims #1 & 2.

The clinician interviews will be conducted and recorded by staff at KPHRI and Brandeis University. The recorded interviews will be transcribed, and the transcriptions will be analyzed by staff at both Brandeis and KPHRI.

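### The operational fall definition counts ambulatory bills, some written by the randomized practices' own unmasked clinicians, while the stated objective covers only ED visits and hospital admissions; this allows falls to be recorded differently between arms

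*Combined protocol and SAP*

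**What the plan says.** The plan gives one operational definition of a fall, in Section 9.4.2 and in the Aim 2 paragraph of Section 3: a fall reason-for-visit "code on ED, ambulatory, or inpatient visit as indicated by a clinician bill (Part B". Ambulatory visits count.

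Elsewhere the outcome is narrower:

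- Section 1.2: "the incidence of emergency department visits or hospitalizations due to a fall during the study window".
- Précis, Design and Outcomes: "a hospital admission, or an emergency department visit for a fall will be assessed at the end of the intervention".
- Section 9.1: "emergency department visits and hospitalizations for a fall".
- Section 10.1: "rates of ED visits or admissions for a fall".
- The Précis objectives and the schedule in Section 6.1 also name only ED visits and hospitalizations.

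On who writes the ambulatory bills, Section 4.1 includes patients only if "They are seen by a clinician at a participating practice as evidenced by one or more evaluation and management claim".

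On what differs between arms, Section 5.1 says of the champion's work: "Typical methods of engagement include educational meetings, facilitating conversations about evidence of harm". The justification text in Section 2 makes the champion a source of information for colleagues on the drugs' harms. Section 4.3 says control clinics have no champion. Section 7.1 states: "These three classes of medication pose significant risks to older patients with dementia including falls". The Study Rationale lists falls first among the documented harms.

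**The concern.** Under the operational definition, some fall codes are entered by the clinicians whose behavior the intervention is meant to change. Intervention-practice clinicians hear about the drugs' harms from a colleague and review patients in order to reduce these drugs. Their champion is also asked to watch for unexpected adverse events (Section 7.2). Each of these is a reason to ask about falls and to code them. Control practices continue usual care.

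Randomization does not protect against this, because the difference arises after assignment. The analysis plan would not reveal it either. Section 9.4.2 names age and sex as covariates, the balance checks in Section 9.5 concern patient mix, and no analysis separates fall codes by setting or by billing practice. If recording rises in one arm, a null or adverse Aim 2 result could not be interpreted.

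**Working it through.** **Plan's own figure.** There is none to reproduce. The documents give no fall rate, expected effect, event count or power for falls. The power figures in Section 9.2 concern the MPR only.

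**Bias formula.** Let s be the share of counted falls captured only by participating-practice bills; a fall also billed from the ED would be found anyway. Let c be the relative rise in fall coding at intervention practices. Then

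observed ratio = true ratio × (1 + s × c).

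Both s and c are assumptions, with s from 10% to 50% and c from 10% to 30%.

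Inflation factor 1 + s × c:

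| | c = 10% | c = 20% | c = 30% |
|---|---|---|---|
| s = 10% | 1.01 | 1.02 | 1.03 |
| s = 25% | 1.025 | 1.05 | 1.075 |
| s = 50% | 1.05 | 1.10 | 1.15 |

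**How large a true reduction to expect.** Section 2.1 gives prevalences of 14.3% for antipsychotics and up to 20% for benzodiazepines. Assume 10-35% for hypoglycemics, users' MPR near 1, and the same fall risk ratio R for each class. The plan's effect of 0.10 SD is then a drop d = 0.10 × √(p(1 − p)): 0.035 for antipsychotics, 0.040 for benzodiazepines, and 0.030 to 0.048 for hypoglycemics. The expected fall ratio is the product over the three classes of

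[1 + (p − d)(R − 1)] / [1 + p(R − 1)].

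- R = 1.3 (assumed): 0.966 to 0.970
- R = 1.5 (assumed): 0.946 to 0.952
- R = 2.0 (assumed): 0.904 to 0.912

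Under these assumptions the plan's own effect size implies about 3-10% fewer falls.

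**Coding rise that would exactly hide a true reduction**, c = (1/true ratio − 1)/s:

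| True ratio | s = 10% | s = 25% | s = 50% |
|---|---|---|---|
| 0.97 | 31% | 12% | 6% |
| 0.95 | 53% | 21% | 11% |
| 0.90 | 111% | 44% | 22% |
| 0.80 | 250% | 100% | 50% |

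**Two examples.** With a true ratio of 0.948, s = 15% and c = 20%, the observed ratio is 0.948 × 1.03 = 0.976, so the reduction is attenuated but still visible. With s = 40% and c = 20%, it is 0.948 × 1.08 = 1.02, so the reduction is hidden. Within the assumed ranges a 20% reduction is never fully hidden: at c = 30% that would need s = 0.25/0.30 = 83%.

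**With ED and inpatient codes only.** If those codes are written by clinicians outside the randomized practices, s = 0 and the observed ratio equals the true ratio.

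**The case against.** Four objections have force.

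1. A reader might infer that the fall outcome as a whole rests on the participating clinics' own coding. It does not. ED and inpatient bills also count and are normally written by other clinicians. Some ambulatory bills will come from outside practices too, since one qualifying claim at a participating practice is enough for inclusion. Only part of the outcome is exposed.
2. The definition requires a fall as the reason for the visit, and the plan calls it the most conservative one available. A fall mentioned during a medication review should not meet it. This limits leakage but may not prevent it, because the plan does not say how the reason for visit is derived from a Part B bill.
3. A reader might infer that intervention clinicians are taught that these drugs cause falls. The curriculum in Table 1 does not mention falls. The documents show harm discussion in one arm only and, separately, name falls as a harm. Linking the two is plausible, but it is an inference.
4. The outcome is secondary, Section 10.1 even calls it exploratory, and Section 9.1 describes a demonstration project. With 2,000 + 500 = 2,500 patients per arm, an assumed fall incidence of 10-30% and clustering ignored, the 95% interval on the ratio is about ±9-17%. A 5% reduction would not be detected even without bias.

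The first three narrow the point, and the fourth limits its consequence. None justifies leaving an arm-dependent recording route in the tested outcome when the stated objective does not call for ambulatory codes.

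**Conclusion.** The concern holds in limited form. The documents disagree on whether ambulatory fall codes count. The version a programmer would implement includes bills from unmasked clinicians of the randomized practices, and harm messaging from a champion exists in one arm only. Differential recording is therefore possible, most likely against the intervention, and no planned analysis would show it.

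Inflation of the intervention-arm count is about 1-15% if s is 10-50% and c is 10-30%. Neither quantity is given in the documents. A true reduction of about 5% could be hidden over much of that range: at c = 30%, s of at least 0.0526/0.30 = 18% suffices. A 10% reduction is hidden only when the clinic-only share is large (at c = 30%, at least 0.111/0.30 = 37%).

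A reader might conclude that the plan will show apparent harm where falls really declined. The documents do not support that. Reversal is one scenario under assumed values, not an expected result. The primary MPR outcome is unaffected.

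**What to change.** In Section 9.4.2 and the Aim 2 text of Section 3, define the tested fall outcome as a fall code on an ED or inpatient visit. This reconciles both sections with the objective as stated in Section 1.2 and elsewhere.

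Report separately by arm, without testing them as the outcome: (a) fall codes on ambulatory bills from participating practices, and (b) ambulatory visits per patient. A difference in (a) without a matching difference in ED and inpatient falls would point to recording rather than occurrence. Item (b) shows whether more contact explains it.

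The work is a filter on claims the study will already hold, plus a few lines of text. The statistical cost is fewer counted falls. If ambulatory-only falls make up 10-50% of the current count (assumed), interval half-widths grow by roughly 1/√(1 − share), that is 1/√0.90 = 1.05 to 1/√0.50 = 1.41. The change removes the ambulatory coding route. It would not remove any change in how readily practices send patients to the ED, and the protocol should say so.
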